#### **12.1.5. Multiple Comparisons**

Alpha splitting will be applied for multiplicity adjustment.

#### **12.2. Subject Disposition, Demographics, and Treatment Adherence**

Subject disposition will be presented for all subjects. The number of subjects who were screened, randomized, started study drug, completed the study, discontinued study drug early, and discontinued from the study early will be provided for Part 1 and for Part 2. The reasons for early discontinuation of study drug and of study will be presented for each part.

Demographic data (age, gender, ethnicity and race) and baseline characteristics will be listed and summarized by randomized treatment group and overall for the ITT Analysis Set.

Adherence to planned study drug dosing will be estimated by drug accountability.

### **12.3. Efficacy**

#### **12.3.1. Efficacy Endpoints**

##### *12.3.1.1. Part 1*

##### *Primary Efficacy Endpoint (Part 1)*

[figure not shown]
- Proportion of subjects with improvement in fibrosis by at least 1 stage (NASH CRN system) AND no worsening of steatohepatitis (no worsening of lobular inflammation or hepatocellular ballooning grade) on liver histology at Month 12 relative to the Screening biopsy

##### *Key Secondary Efficacy Endpoint (Part 1)*

- Proportion of subjects with improvement in fibrosis by at least 2 stages (NASH CRN system) AND no worsening of steatohepatitis (no worsening of lobular inflammation or hepatocellular ballooning grade) on liver histology at Month 12 relative to the screening biopsy

##### *Secondary Efficacy Endpoints (Part 1)*

- Proportion of subjects with improvement in fibrosis by at least 1 stage (NASH CRN system), regardless of effect on steatohepatitis, at Month 12 relative to the Screening biopsy
- Proportion of subjects with improvement in fibrosis by at least 2 stages (NASH CRN system), regardless of effect on steatohepatitis, at Month 12 relative to the Screening biopsy

- Change from baseline to Month 12 in ELF.

#### 12.3.1.2. Part 2

##### *Primary Efficacy Endpoint (Part 2)*

- Time to first occurrence of any of the following adjudicated events:
  - Death (all cause)
  - Histopathologic progression to cirrhosis (defined by NASH CRN Fibrosis Stage 4)
  - Liver transplant
  - MELD score  $\geq 15$
  - Ascites (requiring intervention, ie, large volume paracentesis  $\geq 1L$  or initiation of a diuretic)
  - Hospitalization (as defined by a stay of  $\geq 24$  hours) for onset of: variceal bleed, hepatic encephalopathy (defined by a West Haven Stage of  $\geq 2$ ), spontaneous bacterial peritonitis (confirmed by diagnostic paracentesis with positive ascitic fluid bacterial culture)

[figure not shown]
Each component of this endpoint will be considered by the independent adjudication committee, and only events confirmed by the committee will be included in the primary analysis.

If any of the above events occur in Part 1, they will be included in this primary efficacy endpoint for Part 2.

##### *Secondary Efficacy Endpoints (Part 2)*

- Proportion of subjects with improvement in fibrosis by at least 1 stage (NASH CRN system) AND no worsening of steatohepatitis (no worsening of lobular inflammation or hepatocellular ballooning grade) on liver biopsy at Month 12 relative to the Screening biopsy – (subjects newly randomized in Part 2)
- Proportion of subjects with improvement in fibrosis by at least 1 stage (NASH CRN system), regardless of effect on steatohepatitis, on liver biopsy at Month 12 relative to the Screening biopsy – (subjects newly randomized in Part 2)
- Proportion of subjects with improvement in fibrosis by at least 2 stages (NASH CRN system) AND no worsening of steatohepatitis (no worsening of lobular inflammation or hepatocellular ballooning grade) on liver biopsy at Month 12 relative to the screening biopsy – (subjects newly randomized in Part 2)

- Proportion of subjects with improvement in fibrosis by at least 2 stages (NASH CRN system) regardless of effect on steatohepatitis on liver biopsy at Month 12 relative to the screening biopsy – (subjects newly randomized in Part 2)
- Proportion of subjects with improvement in fibrosis by at least 1 stage (NASH CRN system) AND no worsening of steatohepatitis (no worsening of lobular inflammation or hepatocellular ballooning grade) on liver biopsy at Month 60 relative to the Screening biopsy – (all subjects)
- Proportion of subjects with improvement in fibrosis by at least 1 stage (NASH CRN system), regardless of effect on steatohepatitis, on liver biopsy at Month 60 relative to the Screening biopsy – (all subjects)
- Proportion of subjects with improvement in fibrosis by at least 2 stages (NASH CRN system) AND no worsening of steatohepatitis (no worsening of lobular inflammation or hepatocellular ballooning grade) on liver biopsy at Month 60 relative to the screening biopsy – (all subjects)
- Proportion of subjects with improvement in fibrosis by at least 2 stages (NASH CRN system), regardless of effect on steatohepatitis on liver biopsy at Month 60 relative to the screening biopsy – (all subjects)

- Proportion of subjects with improvement in fibrosis by at least 1 stage (Ishak system), regardless of effect on steatohepatitis, on liver biopsy at Month 12 relative to the Screening biopsy – (subjects newly randomized in Part 2)
- Proportion of subjects with complete resolution of steatohepatitis (defined as histopathologic interpretation of no fatty liver disease or simple or isolated steatosis with no steatohepatitis) AND no worsening of liver fibrosis (defined as progression of NASH CRN fibrosis stage) at Month 60 relative to the Screening biopsy – (all subjects)
- Proportion of subjects with improvement in fibrosis by at least 1 stage (Ishak system), regardless of effect on steatohepatitis, on liver biopsy at Month 60 relative to the Screening biopsy – (all subjects)
- Proportion of subjects with histopathologic progression to cirrhosis (defined by NASH CRN Fibrosis Stage 4) at Month 60– (all subjects)
- Change from baseline in noninvasive assessments of liver fibrosis (including FIB-4, APRI, NFS, ELF and liver stiffness through TE) over time – (all subjects)

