Subjects who progress to cirrhosis or reach a liver-related clinical outcome, which must be adjudicated by an independent adjudication committee, will complete the study and return to the clinic for a Follow-up visit 30 days after the last dose of study drug (Visit 98). After completion of the Follow-up visit (Visit 98), these subjects will become eligible for open-label access to CVC in a separate study (Clinical Study Protocol 3152-201-002).

[figure not shown]
The study design is illustrated in [Figure 1](#) and described briefly in Section 7.1.1 (Part 1) and Section 7.1.2 (Part 2). Study procedures are summarized across all study visits within the Schedule of Assessments for Part 1 ([Table 20–1](#)) and Part 2 ([Table 20–2](#)). Except for the End of Treatment and Follow-up visits, all subsequent visits are based on the Baseline visit date.

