### **11.2. Assessments of Efficacy**

In Part 1, subjects meeting all eligibility criteria and with suspicion of significant liver fibrosis (through clinical, hepatic fibrosis indices, and/or liver stiffness assessment) will have a liver biopsy read by an independent central pathologist during the Screening period. In randomized subjects, a second post-treatment liver biopsy will be collected within  $\pm 2$  weeks of the Month 12 visit.

In Part 2, newly enrolled subjects will undergo a liver biopsy at Screening for assessment of eligibility and a second post-treatment liver biopsy will be collected within  $\pm 2$  weeks of the

Month 12 visit. All subjects (newly randomized subjects with a liver biopsy diagnosis of NASH and Stage 3 liver fibrosis (by NASH CRN system) and those who continue from Part 1) will undergo a liver biopsy at Month 60 (within  $\pm$  2 weeks) after first dose of study drug.

At the end of study, if a subject has received study drug for at least 6 months and has not had the Month 60 biopsy, then a biopsy should be taken within 30 days of the end of study, if feasible.

Liver biopsies will be performed per standard of care (eg, taking into account the subject's health status, coagulation profile, and use of concomitant medications). Subjects who discontinue study drug are encouraged to continue with all other evaluations as scheduled in this protocol, including biopsies and other invasive procedures at the scheduled visits. If a subject discontinues study participation early and has received study drug for at least 6 months in Part 1 or Part 2, then a biopsy should be taken within 30 days of discontinuation, if feasible. All liver biopsies will be evaluated by an independent central pathologist; whenever possible, the same pathologist will evaluate all biopsies from an individual subject. The independent central pathologists will be blinded to individual treatment assignment.

Liver biopsy at Screening and Months 12 and 60 will be used to determine improvement in histologic fibrosis stage (NASH CRN – the system used to assess the primary efficacy endpoint – and Ishak systems).

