Responder	
 • Categorical descriptive statistics for responders and nonresponders 
 ○ Nonresponders include: 
 ▪ Subjects who do not meet responder criteria ▪ Subjects missing the post-baseline liver biopsy will be included as nonresponders (see Section 5.1.1.1.5 for handling of missing biopsy or inadequate biopsy) • Risk differences and Wilson's method for CIs vs Placebo • Estimates derived from Cochran-Mantel-Haenszel (CMH) model controlling for factors (treatment group, fibrosis stage at baseline [2 vs 3] and presence or absence of T2DM at baseline) 
 ○ Mantel-Haenszel (MH) odds ratios (ORs) and 95% CIs vs Placebo ○ P-values comparing treatment group vs Placebo • N1 = all subjects unless otherwise specified
Time-to-event (TTE)	
 • Categorical descriptive statistics for subjects with events and censoring 
 ○ Censoring includes: 
 ▪ Subjects who do not meet event criteria ▪ Subjects with no post-baseline values of corresponding parameters • Quartiles, estimated event rates, and CIs derived from Kaplan-Meier (KM) nonparametric model using log-log transformation of survival function using product-limit method • Estimates derived from Cox proportional hazards model controlling for factors (treatment group, fibrosis stage at baseline [2 vs 3] and presence or absence of T2DM at baseline) 
 ○ Hazard ratios (HRs) and CIs vs Placebo • Estimates derived from stratified log-rank model controlling for factors (treatment group, fibrosis stage at baseline [2 vs 3] and presence or absence of T2DM at baseline) 
 ○ P-values comparing treatment group vs Placebo • N1 = all subjects unless otherwise specified

Methodology	Description
KM figure	
 Step-function figure of cumulative distribution function [1 - survival function] estimates with censoring indicators, derived from KM nonparametric model

CFB = change from baseline; ANCOVA = analysis of covariance; TTE = time-to-event.

Raw and derived data listings will be provided, and will be fully defined in the table, figure, and data listing specification document.

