5.1.1.1.5 Missing Data

General missing data handling conventions are specified for methodologies in Section 5.1.1.1.3 and summarized as follows:

Table 5-4 Missing Data Handling by Endpoint Type

Parameter type	Timing	Missing Data Handling
Responder (Part 1: primary endpoint at Month 12)	Screening, Month 12	
 • All subjects in mITT analysis set included. Subjects with missing baseline biopsy data should not be randomized in the study. • Any available adequate liver biopsy after baseline will be used as the biopsy for the target visit (ie., Month 12), no matter when it was obtained relative to the first dose of study drug. • Subjects with multiple liver biopsies will have the evaluable biopsy closest to the target visit included in the analysis. • Subjects who do not have an evaluable liver biopsy at both Screening and the target visit will be included in the analyses as nonresponders. • Summaries of subjects who do and who do not have evaluable liver biopsies at the target visit will be provided to assess whether demographics, baseline data or safety data are predictive of missingness.

Parameter type	Timing	Missing Data Handling
		
 Subjects who do not have an evaluable biopsy at the target visit will be those with no post baseline liver biopsy or those with a biopsy reading of non-evaluable from the central reader. Sensitivity analyses for the primary efficacy endpoint will be performed, accounting for both missing at random and missing not at random scenarios.
Responder (Part 2: secondary endpoint at Month 60)	Screening, Month 60	
 Same as above for target visit, Month 60

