6.2 Analysis Visit Windows

6.2.1 Efficacy

The analysis visit windows for efficacy endpoints, including liver biopsy, are defined as follows:

Table 6-2 Efficacy Analysis Visit Definitions

Analysis Phase	Analysis Visit (Derived)	Study Visit (eCRF)	Window
Part 1 & Part 2			
Pretreatment	Baseline	Day 1	Treatment Day ≤ 1 , pre-randomization in Part Y
Treatment	Month 12	Day 360	Treatment Day [316, 405], post-randomization in Part 2 Note: For the primary efficacy analysis in Part 1 using the mITT analysis set, any available liver biopsy after randomization will be used for the Month 12 biopsy, no matter when it was obtained relative to the first dose of study drug. Subjects with multiple liver biopsies will have the evaluable biopsy closest to the Month 12 visit included in the analysis.
	Month 60	Day 1800	Treatment Day [1756, 1845], post-dose in Part 2
	End of study	Final or termination visit	Last non-missing assessment during the Treatment Period in Part Y / between Treatment Day 1 in Part Y, post-dose, and Off-treatment Day 1, inclusive, where Y=1, 2.

The following general conventions for repeated or unscheduled assessments will apply unless otherwise specified:

- For scheduled and unscheduled assessments, if more than one assessment is measured within the same visit window, then the record with the latest visit date (from baseline) will be used for that visit window.
- All assessments will be included in respective listings.

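### On the Month 60 cirrhosis endpoint, the missing-biopsy rule scores subjects who leave at a clinical liver outcome or die, without a Stage 4 biopsy, as free of cirrhosis

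*Protocol*

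**What the plan says.** The endpoint, in Protocol 12.3.1.2 for all subjects, is "Proportion of subjects with histopathologic progression to cirrhosis (defined by NASH CRN Fibrosis Stage 4) at Month 60". It counts an adverse outcome.

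Protocol 7.1 ends participation at a liver event: "Subjects who progress to cirrhosis or reach a liver-related clinical outcome, which must be adjudicated by an independent adjudication committee, will complete the study". A subject who leaves this way before Month 60 has no scheduled Month 60 biopsy, and neither does a subject who dies.

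Part 2 binary endpoints are analysed by stratified CMH. The Responder method in SAP Table 5-2 keeps all subjects in the denominator and states: "Subjects missing the post-baseline liver biopsy will be included as nonresponders". SAP Table 5-4 says the same by target visit: "Subjects who do not have an evaluable liver biopsy at both Screening and the target visit will be included in the analyses as nonresponders". Its row for the Part 2 secondary endpoint at Month 60 reads "Same as above for target visit, Month 60".

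Three further provisions bear on the point:

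- Table 5-4 lets another biopsy stand in for the scheduled one, whatever its date: "Any available adequate liver biopsy after baseline will be used as the biopsy for the target visit (ie., Month 12), no matter when". Protocol 12.1.4 likewise uses results as obtained and disregards visit windows.
- SAP Table 6-2 nevertheless defines the Month 60 biopsy as "Treatment Day [1756, 1845], post-dose in Part 2". Its note admitting biopsies from any time is attached only to the Part 1 Month 12 analysis.
- Protocol 11.2 covers subjects who leave early after at least 6 months on drug: "then a biopsy should be taken within 30 days of discontinuation, if feasible". A similar conditional biopsy applies at end of study if the Month 60 biopsy was not done.

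**The concern.** Treating missing as nonresponse is cautious when response is good. When the counted outcome is bad, the same rule becomes optimistic. Nothing visible in either document reverses it for this endpoint. The subjects affected are not a random subset: they include those who developed ascites, had a variceal bleed, reached the MELD threshold, were transplanted or died.

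If the drug works, such exits are more frequent on placebo. Scoring them as cirrhosis-free then removes more apparent progression from placebo than from CVC, and the reported difference understates the true one. If the drug were harmful, the rule would instead flatter CVC.

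The plan deals with this for the Part 2 primary composite, where a subject without a biopsy still counts through any other component (Protocol 12.1.4; SAP Table 5-4). The Month 60 cirrhosis proportion has no such provision.

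**Working it through.** **Step 1. The two SAP tables applied to each type of subject.**

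| Subject | Table 5-4 (any available biopsy) | Table 6-2 (Days 1756 to 1845) |
|---|---|---|
| Stage 4 on a Month 12 or unscheduled biopsy, leaves | Cirrhosis | No biopsy in window: free |
| Non-cirrhotic Month 12 biopsy, later clinical liver event, transplant or death before Month 60, no exit biopsy | Month 12 reading carried: free | Free |
| As above, with an exit biopsy before Day 1756 | Exit reading used | Outside window: free |
| No post-baseline biopsy, leaves or dies | Free | Free |

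The second and fourth rows are scored free of cirrhosis under either table. The first and third depend on which table governs.

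**Step 2. The plan's own figure.** No power is stated for this endpoint, so the check is on the Part 2 primary (Protocol 12.8.2): 367 events, hazard ratio 0.62, 2:1 allocation. By Schoenfeld's formula, sqrt(367 × 2/3 × 1/3) × |ln 0.62| = 9.03 × 0.478 = 4.32. Power is 86.2% at two-sided 0.00125 (stated 85%) and 99.1% at 0.05 (stated 99%). The planning assumptions reproduce.

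**Step 3. Month 60 event proportions on those assumptions.**
- Placebo: 1 − 0.80 = 20.0%, about 133 of 666.
- CVC: 1 − 0.80^0.62 = 12.9%, about 172 of 1334.
- Difference: 7.1 points. SE = sqrt(0.2 × 0.8/666 + 0.129 × 0.871/1334) = 1.8 points. Risk ratio: 0.129/0.200 = 0.65.

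These are rates for the composite, including death and clinical events. They serve only as a scale, because the documents give no cirrhosis rate.

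**Step 4. Assumed share s of events that are exits with no Stage 4 biopsy.** The documents do not give s. Observed proportion = event proportion × (1 − s).

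| s, placebo / CVC | Placebo | CVC | Difference (points) | Risk ratio |
|---|---|---|---|---|
| 10% / 10% | 18.0% | 11.6% | 6.4 | 0.65 |
| 25% / 25% | 15.0% | 9.7% | 5.3 | 0.65 |
| 50% / 50% | 10.0% | 6.5% | 3.5 | 0.65 |
| 25% / 10% | 15.0% | 11.6% | 3.4 | 0.78 |
| 40% / 10% | 12.0% | 11.6% | 0.4 | 0.97 |
| 50% / 10% | 10.0% | 11.6% | −1.6 | 1.16 |

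At 25% in both arms, about 33 placebo and 43 CVC subjects are scored cirrhosis-free.

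**Step 5. Reversal.** With s = 10% on CVC, the arms are equal when 0.200 × (1 − s) = 0.129 × 0.90, so s = 1 − 0.116/0.200 = 42% on placebo.

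**The case against.** The strongest reply has four parts.

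1. A reader might infer that everyone who leaves at a liver event is scored free of cirrhosis, including those who left because of cirrhosis. Table 5-4 and Protocol 12.1.4 do not support that: the Stage 4 biopsy is carried to Month 60 and counts. Only the Table 6-2 window says otherwise, and that is a conflict to resolve. This part stands.

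2. The exit biopsy can supply the missing reading. It can, but it is conditional on feasibility and on 6 months of treatment. It is least likely in a decompensated patient and cannot follow a death. It narrows the gap without closing it.

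3. The governing text may be redacted. The endpoint follows a gap in the Protocol list. It is absent from the synopsis secondary list, the objectives in Protocol 6.2 and the visible list in SAP 4.2, and SAP 5.1.1.3.2 is not visible. Its tier, and therefore the application of the Month 60 responder row, is an inference. This stands as a limit on certainty.

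4. Progression is not hidden from the trial as a whole. These exits are events in the primary composite, and each component, including cirrhosis on biopsy, is to be summarised by arm (Protocol 12.3.2.2; SAP Table 5-14). That is correct, but it does not repair this endpoint's own analysis.

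**Conclusion.** The concern holds for a defined group: subjects who leave at a clinical liver outcome or transplant, or who die, before Month 60 without a Stage 4 reading. Under the visible rules they receive the favourable result, and the arm with more of them looks better than the truth. Separately, Tables 5-4 and 6-2 disagree about exits with biopsy-proven cirrhosis.

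The size is unknown. With assumed equal shares of 10% to 50%, the 7.1-point difference falls to between 6.4 and 3.5 points and the risk ratio stays near 0.65. The lower shares are more plausible if Table 5-4 governs, since biopsy-proven exits are then counted, and the higher ones if Table 6-2 does.

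A reader might infer that the worse arm would come out ahead. The documents do not support that: with equal shares the effect is attenuation, and reversal needs very unequal shares, such as above 42% on placebo against 10% on CVC. The Part 2 primary analysis and its power are untouched. The conclusion assumes that no redacted text sets a different rule for this endpoint.

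**What to change.** Before Part 2 unblinding:

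- State in SAP Table 5-4 that scoring a missing biopsy as nonresponse does not apply to this endpoint, and say how biopsies missing for other reasons are handled.
- Count Stage 4 on any evaluable biopsy up to and including Month 60.
- Align the Month 60 window in Table 6-2 with Table 5-4 and Protocol 12.1.4.
- Do not score subjects who leave at an adjudicated liver event, transplant or death without a Stage 4 biopsy as cirrhosis-free. Report the cumulative incidence of cirrhosis at Month 60 with those exits as competing events. Show the competing-event incidence by arm beside it, because the cirrhosis curve alone does not count those subjects as progressed.
- Add a sensitivity analysis that counts adjudicated liver events and transplant as progression. Keeping this out of the main definition preserves a histologic endpoint and avoids largely repeating the primary composite. Deaths stay as competing events, since no visible text provides for attributing them to liver disease.

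The cost is endpoint and SAP wording and a little more analysis work. No new procedure is needed, and the adjudicated events are already to be collected for the primary endpoint.

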### **12.3.2. Methods of Analysis for Efficacy Endpoints**

[figure not shown]
#### **12.3.2.1. Part 1**

The primary analysis of Part 1 will occur when approximately 1200 randomized subjects have been followed for at least 12 months. Subjects who will contribute to the primary analysis of Part 1 will be identified before unblinding of any subjects for Part 1 analysis; subjects who will not contribute to the primary analysis of Part 1 will be identified by date of randomization and will be determined before randomization. Individual subjects' treatment group assignments will not be disseminated to the sites until the end of Part 2 to allow for continued blinded assessment during Part 2.

For the primary efficacy analysis in Part 1, using the mITT analysis set, any available liver biopsy after baseline will be used as the Month 12 biopsy, no matter when it was obtained relative to the first dose of study drug. Subjects who do not have an evaluable liver biopsy at both Screening and Month 12 will be included in the analyses as nonresponders. Subjects with multiple liver biopsies will have the evaluable biopsy closest to the Month 12 visit included in the analysis.

The proportion of subjects who meet the primary efficacy endpoint in Part 1, and each component, will be summarized by treatment group. Two-sided 95% confidence intervals for the proportion who meet the primary efficacy endpoint, calculated using Wilson's method for CI, will also be reported.

Part 1 testing hierarchy includes 2 tests, one for the primary endpoint and the other for the key secondary endpoint. The key secondary endpoint is tested only when the primary endpoint result is significant. The surrogate endpoint will be tested at 0.0012 (2-sided) level

*12.3.2.2. Part 2*

The primary analysis for Part 2 will occur when adjudicated events have been accrued in 367 unique subjects across Part 1 and Part 2. Because many events may be observed from the Month 60 liver biopsy, and given that all reported events will need to undergo independent adjudication prior to being included or excluded from the analysis, it is possible that more than or fewer than 367 events will be included in the analysis. All subjects and events in the

database at the time of Part 2 database lock and unblinding, and only those events, will be included in the primary analysis of Part 2. If multiple events are observed in a single subject, only the first observed event will be used in the analysis.

For the primary efficacy analysis in Part 2 using the mITT analysis set, any available liver biopsy after baseline will be used for assessment of components of the clinical endpoint that require a biopsy, no matter when obtained. Subjects who do not have an evaluable liver biopsy at both Screening and postbaseline will be included in the analyses as having an event only if they meet a component that does not require a biopsy; otherwise they will be included as not having an event and censored at the last visit. Subjects with multiple liver biopsies will be included as an event if any (one or more) biopsy meets the definition of the primary endpoint, as determined by the adjudication committee.

The proportion of subjects who meet the primary efficacy endpoint in Part 2, and each component, will be summarized by treatment group. Two-sided 95% CIs for the proportion who meet the primary efficacy endpoint, calculated using Wilson's method for CI, will also be reported. Time-to-event analyses will be performed using the Kaplan-Meier product-limit method with tabular and graphical presentation for the cumulative probability of event rate by treatment group. Subjects will be censored for analysis at the last recorded study visit.

Analysis of the primary endpoint of Part 2 will use the logrank test, stratified by randomization strata (fibrosis stage [2 vs 3] and presence or absence of T2DM at Baseline, for a total of 4 strata), to compare the rates in the 2 randomized treatment arms. If multiple adjudicated events are observed in a single subject, only the first observed event will be used in the analysis. The analysis will use the mITT analysis set, with supportive analyses reported for the ITT and PP2 analysis sets. Subjects who do not have an adjudicated event will be censored for analysis at the last recorded study visit. The p-value for the test of no difference between treatment arms (hazard ratio=1) will be presented as well as the hazard ratio from a proportional hazards model (CVC divided by placebo) and corresponding 95% CI. To manifest strong evidence from a single confirmatory study, the hypothesis test of clinical endpoint will be performed at a significance level of 0.00125 (2-sided) if the test of the surrogate endpoint is successful and 0.00005 (2-sided) otherwise. For study success, the hypothesis test of clinical endpoint will be performed at a significance level of 0.05 (2-sided) if the test of the surrogate endpoint is successful and 0.002 (2-sided) otherwise.

Analysis of secondary efficacy endpoints of Part 2 will use similar methods to the primary endpoint analysis in Part 2. The primary endpoint in Part 1, improvement in fibrosis by at least one stage and no worsening of steatohepatitis at Month 12, will be reported for subjects not in the Part 1 analysis (subjects newly randomized in Part 2), and for all subjects in the study (Month 12 results from Part 1 and Part 2 combined). Results for the mITT and PP2 analysis sets will be reported for the secondary endpoints in Part 2. Binary endpoints will be analyzed with the CMH procedure, stratified by randomization strata. Continuous endpoints will be analyzed with analysis of covariance, with randomization strata included as covariates. Time to event endpoints will be analyzed with the stratified logrank test, stratified by randomization strata.

